2.2 Statistical Software and Quality Control

All statistical analyses will be performed using SAS® version 9.3 or higher. Tables, figures and data listings will be generated in Microsoft® Word® as well as PDF® format.

Quality control of SAS® programs will include a review of the whole process of result generation:

- Review of all analysis SAS® programs
- Review of SAS® log for errors, warnings and other notes that could indicate mistakes in the programs
- Review of all tables, listings and figures for completeness and correctness

As additional quality control measure, independent re-programming will be performed as described in SOP SAS04.

2.3 Applicable Standard Operating Procedures

The applicable Standard Operating Procedures (SOPs) of [REDACTED] for this study are:

STAT01 Statistical Analysis File

STAT03 Statistical Analysis Plan

STAT04 Interim Analysis

STAT05 Randomization and Unblinding

STAT06 Data Review Meeting

STAT07 Report Writing

SAS01 SAS General Principles

SAS04 Handling of Statistical Analyses

SAS06 CDISC- ADaM

SAS07 CDISC - Quality Control

2.4 Blinding and Randomization

Subjects will be allocated to treatment groups via the EDC system. Eligible subjects will be randomized stratified by study site 1:1:1:1 in the Run-in Phase and stratified by study site, age group and baseline *B.b. s.l.* serostatus 2:2:1 in the Main Study Phase according to a randomization list created by a statistician. The study will be an observer-blinded trial, which will be conducted in a blinded manner for the study investigators, the sponsor including laboratory personnel, and the subjects. Only designated study staff who randomize subjects into treatment groups and perform preparation and application of the vaccinations will be unblinded. These unblinded study staff members will not be involved with trial conduct otherwise. An overview of persons who will be unblinded is provided below:

Unblinded:

- Designated study site staff who randomize subjects to treatment groups and are concerned with IMP handling (i.e. perform preparation and application of the study vaccine, maintain drug dispensing log detailing the dates and quantities of IMP administered to each subject). These unblinded study staff members will not be involved with trial conduct otherwise.
- CRAs responsible for monitoring of IMP handling and related data for verifying drug accountability during the study and performing overall drug accountability.
- Statistical team at the CRO performing statistical analyses for generation of safety data tables for the DSMB.
- DSMB members.

Blinded:

- Study participants
- Investigators and other study staff involved in general study conduct and safety assessments.
- All other CRAs (responsible for monitoring study data apart from IMP handling/drug accountability).
- All other sponsor and CRO staff including laboratory personnel at the sponsor's labs for immunogenicity assessments.

General unblinding of sponsor staff and ADMB will be done for the IA Day 85 after confirmation that all subjects performed Visit 6 or, in case of missing V6 visits, after the close of the time window for Visit 6. Interim analyses results will be distributed to selected sponsor representatives.

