2. GENERAL CONSIDERATIONS

2.1 Conduct of Analysis

An interim analysis (IA) on safety and immunogenicity data will be conducted in two parts after the last subject completed Visit 6 (i.e. Day 236). The first part (IA Day 85) will be performed after safety data up to Day 85 have been cleaned and immunogenicity samples of Day 1 and 85 have been analyzed. The first part (IA Day 85) will cover safety data up to Visit 4 (Day 85) and ELISA immunogenicity data from Visit 1 (Day 1) and Visit 4 (Day 85). The second part (IA Day 236) will cover safety data up to Visit 6 (Day 236, i.e. six months after the last vaccination).

Data from selected dose groups in the Main Study and data from respective dose groups from the Run-in phase will be pooled for this and all further analyses.

A preliminary immunogenicity analysis was done prior to the IA D 85 as described above. This analysis was described in a separate analysis plan and covered descriptive immunogenicity analysis of selected time points of subjects from the run-in phase only.

A final data analysis will be conducted once the last subject has completed the study, i.e. Visit 7 (Month 12). As part of this analysis, Serum Bactericidal Assay (SBA) results will be analyzed. Those results will only be available for a subset of subjects, that was randomly chosen from the set of subjects from the main phase who have both a Day 1 and Day 85 immunogenicity blood sample.

It is indicated in Section 7, which Tables, Listings and Figures (TLFs) are provided for IA D85 and IA D236.

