2.14 Changes in the Conduct of the Study or Planned Analysis

Statistical analysis will be conducted as described in this SAP. Any deviations or changes will be described and justified in the CSR.

- It was stated in the protocol that an interim analysis on safety and immunogenicity data will be performed after all subjects have completed Visit 6 (i.e. Day 236, six months after the last vaccination) and that this interim analysis will cover safety and immunogenicity data up to Visit 4 as well as safety data up to Visit 6. This interim analysis will be conducted in 2 parts, a IA Day 85 covering all safety data up to Day 85 and immunogenicity data from Day 1 and Day 85. The second part will cover all safety data up to Day 236 (see Section 2.1). The first part of the Interim Analysis only starts after the last subject completed Visit 6 or the time window for Visit 6 has elapsed.

- The following adjustments concerning statistical analysis as compared to descriptions in the protocol are included in this SAP: The protocol planned to only compare the two dose groups selected for the main phase and the placebo group. However, it was decided to include all dose groups in the comparison. In particular, the pair-wise comparison between the two dose groups selected for the main phase and the placebo group, respectively, will be part of the comparisons that will be performed.
- It was stated in the protocol that all time points up to Day 85 will be included in interim immunogenicity analysis. However, only Day 1 and Day 85 will be analyzed in the IA Day 85. All time points will be analyzed in the Final Analysis.
- Due to optimization of the ELISA assay, the definition for seroconversion for ELISA results was adjusted as compared to the protocol, see Section 5.2.
- Functionality of antibodies will be measured by a Serum Bactericidal Assay (SBA). Analysis of SBA parameters will be described in a separate SAP and is not part of the interim analysis described here.

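### Section 2.4 unblinds sponsor staff generally at IA Day 85 without excepting the immunogenicity laboratory or the later deviation review, although samples and deviations are still open

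*SAP*

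**What the plan says.** **Who is blinded.** SAP Section 2.4 describes the study as blinded for the investigators, "the sponsor including laboratory personnel, and the subjects". Its list of blinded parties repeats the point: "All other sponsor and CRO staff including laboratory personnel at the sponsor's labs for immunogenicity assessments".

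**When that ends.** The closing paragraph of the same section says: "General unblinding of sponsor staff and ADMB will be done for the IA Day 85". The trigger is that every subject is confirmed to have had Visit 6. Where Visit 6 is missing, the close of its window serves instead. The paragraph names no group of sponsor staff that stays blinded. It adds: "Interim analyses results will be distributed to selected sponsor representatives".

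**What must be finished by then.** Under Section 2.1, IA Day 85 needs the Day 1 and Day 85 ELISA samples and safety data cleaned to Day 85. Section 2.14 confirms that the other ELISA visits come later: "All time points will be analyzed in the Final Analysis". Section 5 says that IA Day 236 has no immunogenicity analysis. On the SBA, Section 2.1 says of the final analysis: "As part of this analysis, Serum Bactericidal Assay (SBA) results will be analyzed". Section 2.14 assigns the SBA to a separate SAP.

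**Deviation review.** Section 2.10.3 has the Per-Protocol population defined at a blind data review meeting before IA Day 85. It plans a second meeting before the final analysis for deviations after the interim. That second meeting is not described as blind.

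**The concern.** Laboratory personnel are blinded so that handling and acceptance of a sample cannot depend on knowing its treatment group. Section 2.4 sets up that protection. Its last paragraph, followed as written, lifts it while laboratory work remains to be done.

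At stake are secondary results: persistence of the ELISA response up to Month 12 (GMTs, seroconversion rates and fold rises in Section 1.3.2) and the supportive SBA data.

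The second data review raises the same issue. Section 2.8 has deviations classified case by case and includes an open category for anything that may affect the immune response. That is a judgement, and Section 2.4 would let sponsor participants make it knowing the allocation.

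**Working it through.** The SAP states no figure on this point. The check compares the blinding text with the analysis schedule and adds simple arithmetic on visit days.

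**1. Does the unblinding reach the laboratory?** Section 2.4 twice places laboratory personnel inside the blinded sponsor group. The unblinding sentence covers sponsor staff generally and excludes nobody. By the section's own grouping, the laboratory is covered, although the sentence does not name it.

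**2. What is still open at the trigger?**

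| Item | Needed for IA Day 85? | Reported |
|---|---|---|
| ELISA Day 1, Day 85 | Yes | IA Day 85 |
| ELISA Day 29, 57, 180, 236 | No | Final analysis |
| ELISA Month 12 | No | Final analysis |
| SBA (random subset of Main Study subjects with Day 1 and Day 85 samples) | No | Final analysis |
| Deviations after the interim | No | Second data review, before the final analysis |

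Of the 7 ELISA time points, 2 are covered by IA Day 85 and 7 − 2 = 5 are reported only later. Reporting date is not assay date. The SAP does not say when the Day 29, 57, 180 and 236 samples or the SBA samples are run, so 5 is an upper limit on the time points exposed.

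**3. Which samples cannot have been assayed by then?** Only those not yet drawn. For the last subject:

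- Nominal gap from Visit 6 to Visit 7: 365 − 236 = 129 days.
- Shortest gap within the visit windows of Table 3 (Visit 6 +7/−14 days, Visit 7 ±14 days): (365 − 14) − (236 + 7) = 351 − 243 = 108 days.
- Longest gap within them: (365 + 14) − (236 − 14) = 379 − 222 = 157 days.

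A subject whose Day 1 was *k* days before the last subject's has a nominal Month 12 draw 129 − *k* days after the trigger. If unblinding happened on the trigger date, every subject with *k* < 129 would be drawn after it. Each day of delay before unblinding reduces that limit by one day. The SAP gives neither enrolment dates nor an unblinding date, so the number of subjects cannot be computed.

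**4. Is the primary result exposed?** No. Day 1 and Day 85 samples must be analysed before IA Day 85, and the Per-Protocol population is set at the blind review before it.

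**The case against.** **The laboratory is not named in the unblinding sentence.** True. Where Section 2.4 means to include the laboratory elsewhere, it says so. A reader might infer that the SAP deliberately unblinds the laboratory, and the text does not show that intent. It shows a general rule without an exception, applied to a group that the section has already defined to include the laboratory.

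**Other documents may keep the laboratory masked.** Possible. Section 2.3 lists SOPs on interim analysis and on randomization and unblinding, and a protocol or laboratory plan may provide for coded samples. Missing laboratory detail would be no finding. But the SAP itself sets the scope of unblinding here, and as worded it would cut across any such safeguard.

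**Results go only to selected representatives.** A reader might see this as contradicting general unblinding. It does not: one sentence concerns who may know allocation, the other who receives results. Nor does it protect the laboratory.

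**Many later samples may already be assayed.** This stands. Section 2.1 reports a preliminary analysis of selected time points in Run-in subjects. It would be wrong to say that all five later time points will be tested unblinded.

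**The endpoint rules are objective.** Partly. Section 5.2 fixes the 40 U/mL limit, the 20 U/mL replacement and the seroconversion definition. These act on reported values. The SAP does not describe repeat or run-acceptance rules, so the route from knowledge to bias is a general assumption about laboratory assays and not something the document shows.

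**Safety follow-up.** A reader might infer that safety assessment loses its blind. The text does not support that. Participants, investigators and site staff assessing safety are on the blinded list and are not named in the unblinding. Solicited events, collected for seven days after each vaccination, are complete well before the trigger.

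**Conclusion.** The point holds as a wording fault with an avoidable bias risk. Followed literally, Section 2.4 allows Month 12 ELISA samples drawn after unblinding to be tested by unblinded laboratory personnel, together with any Day 29, 57, 180, 236 or SBA samples still unassayed. It also allows the second data review to classify deviations with allocation known.

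The exposure is limited to secondary ELISA time points, SBA results (not among the endpoints in Section 1.3) and post-interim deviations. Whether the second review can alter the Per-Protocol population is not stated.

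The certainty about Month 12 samples assumes that unblinding follows the last Visit 6 within the nominal 129 days (108 to 157 days across the visit windows). The size of any bias cannot be computed. This is a cheap improvement and does not put the dose choice in doubt.

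**What to change.** Limit the unblinding sentence in Section 2.4 so that:

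- sponsor decision-makers and the ADMB may be unblinded for IA Day 85, as planned;
- laboratory personnel performing ELISA and SBA stay blinded to subject-level treatment allocation until all ELISA and SBA results are final;
- deviations arising after the interim analysis are classified by reviewers without access to allocation, with a matching line in Section 2.10.3 for the second data review meeting.

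If an SOP or laboratory plan already keeps the laboratory masked, a cross-reference plus the word change is enough. Keeping all site-facing sponsor staff blinded to final lock is more debatable and is not needed for this point.

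The cost is SAP wording and access control for a few staff until the final data are locked. Neither the interim analysis nor the dose decision is delayed.

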2.5 Descriptive Analyses

In general, descriptive analyses of continuous variables (summary statistics) will be described with the number of non-missing observations, arithmetic mean, standard deviation (\pm SD), median, quartiles (Q1 and Q3) and range (minimum and maximum).

Descriptive analyses of continuous immunogenicity variables (i.e. tables for the GMT and GMFR) will be described with the number of non-missing observations, geometric mean, confidence intervals for the geometric mean, standard deviation of logarithmic values, median, quartiles (Q1 and Q3) and range (minimum and maximum).

Categorical variables (frequency statistics) will be described with the number of non-missing observations and percentages (%). Percentages will be calculated on the total number of non-missing observations, if not stated otherwise.

2.6 Center and Country Effect and Stratification Variables

The center and region effect will be taken into account and estimated by adding study site and region, respectively in ANOVA models. Also other covariates will be used as described in Section 5.3.

Furthermore, selected tables will be presented per study site/region and by other stratification factors. A separate column in the List of Tables (Section 7) defines which tables will be stratified by study site, region (Europe vs. United States), *B.b. s.l.* serostatus at Visit 0, and by age group as marked in Section 7.

2.7 Handling Missing Data

[figure not shown]
Generally, missing values of immunogenicity variables will not be imputed, and the analyses will be limited to observed values. For missing data in AE evaluation (e.g. missing information if serious, medically attended, about severity or causality) a worst case approach will be applied. In case of missing assignment to solicited or unsolicited, this AE will neither be counted in tables for solicited AEs nor in tables for unsolicited AEs but in tables for all AEs.

2.8 Protocol Deviations

Protocol deviations will be reviewed in the Blind Data Review Meeting (BDRM) prior to interim analysis of D85. Deviations will be classified as minor or major deviations, based on the potential influence on the immunogenicity analysis.

Major protocol violations that lead to exclusion of a subject from the PP Population (see Section 2.10.3) will include but are not limited to the following:

- Subjects who received less than three vaccinations
- Subjects who received wrong vaccinations

- Subjects with substantial time window violations on vaccination visits (Visits 2 and 3)
 - Visit 2 (Day 29): +/- 7 days
 - Visit 3 (Day 57): +/- 10 days
- Subjects who fulfil exclusion criteria 2, 8, 9 and 14
- Subjects with other deviations that may affect immune response

Protocol deviation classification will be made on a case by case decision.

2.9 Exclusion of Time Points in the Per-Protocol Analysis

In the PP analysis immunogenicity samples that are outside the predefined time windows described below will be excluded at the respective visit (exclusion of subjects from the PP Population is described in Section 2.8):

- Visit 2 (Day 29): +/- 7 days
- Visit 3 (Day 57): +/- 10 days
- Visit 4 (Day 85): +/- 10 days
- Visit 5 (Day 180): +/- 14 days
- Visit 6 (Day 236): +/- 21 days
- Visit 7 (Day 365): +/- 28 days

2.10 Analysis Populations

2.10.1 Safety Population

The Safety Population includes all subjects who entered into the study and received at least one vaccination. The Safety Population will be used for all safety analyses as well as demographic data. All analyses based on the Safety Population will be carried out using the actual treatment received. Subjects with vaccination errors will be allocated to a treatment group for safety analyses after a case-by-case review in the BDRM; applying the following general rules:

- If a subject received different VLA15 doses at different visits, the minimum dose received will decide the treatment group of the subject for safety analysis;
- If a subject received both VLA15 and placebo, the subject will be analyzed in a VLA15 group (dose decided by the first rule)

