1.4 Sample Size Calculation

The sample size for the Run-in phase has been chosen to allow detection of common AEs with the three initial dose levels. 30 Subjects will provide 95 % confidence that an AE not seen in the Run-in phase would have a true incidence of below 10 %.

The overall group size for the two doses (VLA15 w/ alum 135 µg and VLA15 w/ alum 180 µg) evaluated in the Main Study phase has been selected to provide a sufficient safety database and for determining the optimal dose before advancing the vaccine candidate into Phase 3. Upon completion of the study, the total number of subjects exposed to the dose used for Phase 3 trials would be a minimum of approximately N=210. The database would thus allow 95 % confidence that a given reaction would not be observed at a higher rate than 1:(210/3) rate, i.e. 1.4 %, if it is not observed in the trials preceding Phase 3.

[figure not shown]
With respect to the primary endpoint, GMTs for ST1-6 specific IgGs on Day 85: In the absence of an established protective titer, sample size calculation is based on somewhat arbitrary differences in GMTs between VLA15 treatment groups, in order to demonstrate which titer levels could be distinguished with the proposed sample size. Titers observed in Phase 1 were used as basis: In the 90 µg w/ alum group (i.e. the lowest dose group used in the present Phase 2 study), a GMT of 61.3 was observed for ST1 (i.e. the serotype with lowest titers in Phase 1) with a Standard Deviation (LOG10) of 0.51. A total of 189 subjects per group (assuming 10 % of the 210 subjects per treatment group are excluded from primary Per-protocol (PP) analysis) will provide 80 % power at a two-sided alpha level of 5 % to distinguish a GMT of 61.3 in one treatment group from a putative higher GMT of 86.1 in another dose group. An approximately 1.5 fold higher titer could thus be distinguished. A 1.5 fold difference in GMTs is often considered a relevant difference in vaccine studies, e.g. when setting non-inferiority boundaries.

The overall sample size of 120 subjects in the placebo group has been selected to allow for the internal validation of both safety and immunogenicity results.

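### For subjects given different VLA15 doses, the minimum-dose rule counts events after the higher dose in the lower-dose safety column, even in vaccination-period tables where the dose given is known

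*SAP*

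**What the plan says.** SAP Section 2.10.1 states the principle first: "All analyses based on the Safety Population will be carried out using the actual treatment received". It then deals with dosing errors: "Subjects with vaccination errors will be allocated to a treatment group for safety analyses after a case-by-case review in the BDRM". Two general rules follow.

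- If the VLA15 dose differed between visits, "the minimum dose received will decide the treatment group of the subject for safety analysis".
- A subject who received both VLA15 and placebo goes to a VLA15 group, with the dose set by the first rule.

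Section 2.8 explains the meeting: "Protocol deviations will be reviewed in the Blind Data Review Meeting (BDRM) prior to interim analysis of D85". Section 2.4 limits the unblinded roles to site staff handling the vaccine, the monitors of that handling, the CRO statistical team preparing DSMB tables, and the DSMB. The blinded list ends with "All other sponsor and CRO staff including laboratory personnel at the sponsor's labs for immunogenicity assessments". General unblinding of sponsor staff comes with IA Day 85.

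Section 2.12 gives every table one column per treatment group. Section 7.1.4 lists safety tables by vaccination period (14.1.4.5 and 14.1.4.33 to 14.1.4.40), by diary day (14.1.4.41 to 14.1.4.43), and by vaccination or diary period for reaction size, fever and number of days (14.1.4.44 to 14.1.4.47). None of these is said to use the dose given in that period, and no sensitivity table for mixed-dose subjects is planned.

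**The concern.** A mixed-dose subject has no single actual treatment, so a whole-study table needs some tie-break. A vaccination-period table does not, because each period starts with one injection of one dose. Carrying the minimum-dose label into those tables puts an event that followed a higher dose under a dose the subject did not receive in that period. This departs from the section's own principle.

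The misplacement has a fixed direction. An event after the higher dose can leave the higher-dose column, but no event in a mixed-dose subject can ever be counted there. In a dose-finding trial this can understate reactions at the higher dose and overstate them at the lower one. It matters most for rare or severe events and for the small 90 µg column.

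The second issue is who applies the rule. Finding the minimum dose requires knowing the doses, and the plan links the allocation to a meeting whose members are meant not to know them.

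**Working it through.** **Inputs.** Section 1.4 gives about 210 subjects per main dose (30 Run-in plus 180 Main Study, Section 1.2). The 90 µg group has 30, from the Run-in phase only. The SAP does not give the number of mixed-dose subjects, so I assume k between 1 and 10.

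**The plan's own figures.** Section 1.4 states bounds of 1.4 % for 210 subjects and below 10 % for 30.

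- 210 subjects: 3/210 = 1.43 %; exact, 1 − 0.05^(1/210) = 1.42 %.
- 30 subjects: exact, 1 − 0.05^(1/30) = 9.5 %.

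Both reproduce. They confirm the group sizes; the point below does not change them.

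**Weight of one subject.** 1/210 = 0.48 %. In the 90 µg column, one added subject with an event is 1/31 = 3.2 %.

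**Rare event.** Suppose k subjects randomised to 180 µg each receive 135 µg once, each has the same reaction after a 180 µg injection, and nobody else has it.

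| k | Minimum rule, 135 µg | Minimum rule, 180 µg | By highest dose, 135 µg | By highest dose, 180 µg |
|---|---|---|---|---|
| 1 | 1/211 = 0.47 % | 0/209 | 0/210 | 1/210 = 0.48 % |
| 5 | 5/215 = 2.33 % | 0/205 | 0/210 | 5/210 = 2.38 % |
| 10 | 10/220 = 4.55 % | 0/200 | 0/210 | 10/210 = 4.76 % |

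Under the minimum rule the apparent dose pattern is reversed, although every reaction followed 180 µg.

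**Common event.** Assume true rates of 10 % at 135 µg and 15 % at 180 µg, with mixed-dose subjects at 15 %. The 135 µg column then shows (210 × 0.10 + k × 0.15)/(210 + k).

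- k = 1: 21.15/211 = 10.02 %, a difference of 4.98 points instead of 5.00.
- k = 10: 22.5/220 = 10.23 %, a difference of 4.77 points.

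Common-event comparisons barely move.

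**The meeting.** Section 2.8 places the BDRM before IA Day 85. Section 2.4 puts general unblinding at IA Day 85 and does not list meeting members among the unblinded. Section 2.10.1 makes the allocation "after a case-by-case review in the BDRM". No section says how the doses reach that meeting, or gives the task to the unblinded CRO team.

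**The case against.** The strongest defence is that some rule is needed, that the minimum is a dose the subject did receive, and that it was fixed in advance. Assigning by highest dose has the mirror-image fault, since events after the lower dose would then appear under the higher one. This stands for whole-study tables, where the choice is a trade-off. It does not cover vaccination-period tables, where no trade-off is needed.

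It can also be said that the listings already allow tracing. Listing 16.2.1.1.1 shows planned and actual treatment, 16.2.1.1.4 shows each vaccination with kit number, 16.2.1.1.8 shows deviations, and the AE listings give onset relative to vaccination. That helps only in part. The vaccination listing specifies neither dose nor volume. If actual treatment is filled by the minimum-dose rule, a subject planned for 135 µg who once received 180 µg shows the same planned and actual treatment. No listing re-attributes events in the tables.

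On the meeting, the wording allows a blinded review of the error with the rule applied afterwards by someone else, and an unblinded CRO team exists. What remains is that the plan does not assign that step.

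A reader might infer three stronger things, which the document does not support.

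- That the two rules contradict each other. They do not: the second uses the first. Together they keep anyone exposed to VLA15 out of the placebo column and take the lowest dose among VLA15 doses.
- That the 1.4 % statement in Section 1.4 is falsified. Its condition is "if it is not observed in the trials preceding Phase 3". That refers to the trials, and an event moved between columns is still observed in the trial.
- That Per-Protocol decisions are materially biased. Section 2.8 already lists wrong vaccinations as a ground for exclusion whichever dose was given, and the mITT analysis follows the allocated group.

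**Conclusion.** The point holds in a limited form. The minimum-dose rule moves events after a higher VLA15 dose into the lower-dose column, in that direction only, and without need in tables by vaccination or diary period. The size is probably small: about 0.5 percentage points per affected subject in a group of 210 and about 3 points in the 90 µg group. The number of such subjects is unknown, and the range of 1 to 10 is an assumption. The rare-event table also assumes that every mixed-dose subject reacts after the higher dose and that no one else reacts.

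Safety is a secondary objective. The primary endpoint is the Day 85 titer, analysed primarily in the Per-Protocol Population, so the primary result is not touched. The blinding part is a gap in assigning a task; the document does not show that the blind was broken. This is a worthwhile improvement to the plan and not a threat to its conclusions.

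**What to change.** - **Vaccination-period and diary-period tables:** count each subject under the dose actually given at that vaccination.
- **Whole-study tables:** keep a rule stated in advance, and add one sensitivity table by highest VLA15 dose received.
- **Listings:** flag mixed-dose subjects and show the dose given at each visit. The dispensing log described in Section 2.4 is a natural source.
- **Who applies it:** have the unblinded CRO statistician apply the fixed rule outside the BDRM, and say so in Section 2.10.1. The meeting can still review the fact of a dosing error without the dose.

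The cost is SAP wording, one treatment variable per vaccination period and one extra table. Denominators will differ slightly between periods, which a footnote can explain. The sensitivity table will show some events after a lower dose under the higher one, so it should be read beside the main table and not replace it.
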